8.7. Data Monitoring Committee

Formal safety data reviews will be conducted by the study team (eg, medical monitor, clinical scientist, and biostatistician) and an independent internal review committee at least every 6 months. Details regarding data monitoring will be addressed in the Data Safety Monitoring Charter.

8.8. Product Complaints

The sponsor collects product complaints on study drugs and drug delivery systems used in clinical studies in order to ensure the safety of study participants, monitor quality, and facilitate process and product improvements.

All product complaints associated with material packaged, labeled, and released by the sponsor or its designee will be reported to the sponsor. All product complaints associated with other study material will be reported directly to the respective manufacturer.

The investigator or his/her designee is responsible for reporting a complete description of the product complaint via email or other written communication to the sponsor contact or respective manufacturer as noted in the packaging information. Any AE associated with a product complaint should be reported as described in Section 8.1.2 of this Protocol.

If the investigator is asked to return the product for investigation, he/she will return a copy of the product complaint communication with the product.

9. STATISTICS

9.1. Study Populations

The full analysis set includes all subjects enrolled in the study who received at least 1 dose of study drug (INCAGN01876). This population will be used in the analyses of demographic, baseline, safety, study drug administration, and efficacy data.

[REDACTED]

[REDACTED]

9.2. Selection of Sample Size

9.2.1. Sample Size for Phase 1

The primary objective of Phase 1 of the study is to determine the DLTs and RP2Ds of INCAGN01876 when given in combination with immune therapies. The total number of subjects will depend on the number of dose levels tested before the RP2D(s) are established. Dose escalation will follow the 3 + 3 + 3 design algorithm. The 3 + 3 + 3 algorithm is described as follows: In each treatment group, the first 3 evaluable subjects enrolled within an INCAGN01876 dose cohort will be observed for the specified DLT observation period before the next dose cohort begins enrollment. If 0 DLTs occur in a cohort of 3 evaluable subjects, a new cohort of 3 evaluable subjects will be treated at the next higher dose level. If 1 of 3 evaluable subjects experience a DLT, that cohort will be expanded to 6 evaluable subjects. If 1 of 6 subjects experiences a DLT, a new cohort of 3 evaluable subjects will be treated at the next higher dose level. If 2 of 6 subjects experience a DLT, that cohort will be expanded to 9 evaluable subjects. If 2 of 9 subjects experience a DLT, a new cohort of 3 evaluable subjects will be treated at the next higher dose level. Based on this algorithm, a minimum of 3 evaluable subjects will be enrolled in each cohort with a maximum of 9 evaluable subjects in each cohort.

A range of up to 54 evaluable subjects in each treatment group (9 subjects per dose level for 6 dose levels, if dosing begins with INCAGN01876 0.1 mg/kg), or if a higher starting dose is used based on available safety data from the monotherapy trial (INCAGN 1876-101), then up to 36 evaluable subjects in each treatment group (9 subjects per dose level for 4 dose levels, if dosing begins with 3 mg/kg) will be included based on the dose escalation.

The probabilities of dose escalation from a given dose level for the various DLT rates are provided in [Table 18](#).

Table 18: Probability of Dose Escalation for Various DLT Rates

True DLT Rate	Probability of Dose Escalation
20%	78.4%
30%	56.1%
40%	35.0%
50%	18.9%
60%	8.8%

For example, if the true DLT rate is 50% at a given dose level, there is an 18.9% chance that the dose would be escalated. Further, if the true DLT rate is 20%, there is a 78.4% chance that the dose would be escalated. If the MTD is not determined at the highest dose level tested during the study, then the MTD is at or above the highest dose level. The MTD is below the lowest dose level of INCAGN01876 if the Cohort 1 dose is not well-tolerated.

9.2.2. Sample Size for Phase 2

Phase 2 will further evaluate the safety, tolerability, preliminary efficacy, [REDACTED] of the recommended dose of INCAGN01876 in combination with immune therapies as part of doublet and triplet drug expansion cohorts. In Phase 2, a Simon 2-stage design will be run for the cervical cancer, gastric cancer, SCCHN and PD-1/PD-L1 relapsed melanoma cohorts within a given doublet or triplet treatment group. A Simon 2-stage design with an expansion stage will be used for the PD-1 refractory SCCHN cohort.

The sample size for each tumor type within a given doublet or triplet expansion cohort will be guided by the Simon 2-stage design (except for the PD-1 refractory SCCHN cohort in Treatment Group F). The planned Simon 2-stage designs are summarized in Table 19. Each Simon 2-stage design will have a stopping rule to allow early termination of a particular tumor type within the given treatment combination at the end of Stage 1 if there is insufficient response observed (calculated response rate $< p_0$), while enrolling enough subjects to predict possible target responses ($\geq p_1$) worthy of cohort expansion and potentially further evaluation in future studies. The individual Simon 2-stage designs run for each tumor type within each doublet or triplet expansion cohort will have design parameters that are determined by historical response rates. The same Simon 2-stage design parameters will be used for alternative dosing sequences in the same tumor type and treatment combination. For example, the gastric cohorts in Treatment Groups F, G, and H will all use the same Simon 2-stage parameters.

In order to determine whether the target response rate (p_1) is likely, an initial number of evaluable subjects (n_1 subjects) treated at the MTD or PAD and schedule of INCAGN01876 within the corresponding doublet or triplet expansion cohort will be enrolled in a cohort (Stage 1). If there are r_1 or fewer responses in the cohort, it will be concluded that the true response rate is unlikely to be greater than or equal to the target rate, and no more subjects will be enrolled in that tumor type in Stage 2. In the cohorts in which greater than r_1 responses are observed among the Stage 1 subjects, n_2 additional evaluable subjects will be treated in Stage 2 to estimate the response rate. At the end of Stage 2, if $\leq r$ subjects have responded among the n evaluable subjects, the doublet or triplet schedule will be declared nonpromising for that cohort.

In other words, after the study is finished, if there is a sufficient number of responses in the 2 stages combined, the study doublet or triplet is considered promising; otherwise it is considered nonpromising. The detailed calculations for each tumor type-specific doublet and triplet cohort are based on a 1-sided Type I error of 0.05 and power of 85%. The individual p_0 and p_1 values for the tumor types within doublet or triplet expansion cohorts are listed in Table 19.

For the PD-1 refractory SCCHN cohort in Treatment Group F, a Simon 2-stage design with an expansion stage, as summarized in Table 20, will be used. The definitions of p_0 , p_1 , r_1 , n_1 , and n_2 are the same as those in Table 19. At the end of Stage 2, if r_2 or fewer responses are observed in $n_1 + n_2$ subjects, the PD-1 refractory SCCHN cohort will be terminated early for futility. If more than r_2 responders are observed, an additional n_3 evaluable subjects will be enrolled in the expansion stage. At the end of the expansion stage, if $\leq r$ subjects have responded among the n evaluable subjects, the concurrent dosing strategy of INCAGN01876 and nivolumab will be declared nonpromising for the PD-1 refractory SCCHN cohort. In other words, after the study is finished, if there is a sufficient number of responses in the 3 stages combined, the doublet schedule of INCAGN01876 and nivolumab will be considered promising for the PD-1 refractory SCCHN cohort; otherwise it is considered nonpromising. With this 3-stage design, the 1-sided Type I error is 0.0231, and the power is approximately 88%.

Formal quarterly safety reviews will be conducted to review efficacy and safety data with the obligation to hold a safety review meeting every 6 months.

Table 19: Planned Simon 2-Stage Designs for Phase 2

Indication	Combination	r_1	n_1	r	n_2	n	p_0	p_1
SCCHN	GITR + Nivo	3	16	10	30	46	15%	35%
Gastric	GITR + Nivo	3	16	10	30	46	15%	35%
Cervical	GITR + Nivo	4	17	14	34	51	20%	40%
Relapsed melanoma	GITR + Nivo	2	20	8	30	50	10%	25%
Relapsed melanoma	GITR + Ipi	2	20	8	30	50	10%	25%
SCCHN	GITR + Nivo + Ipi	5	18	17	32	50	25%	45%
Gastric	GITR + Nivo + Ipi	5	18	17	32	50	25%	45%
Cervical	GITR + Nivo + Ipi	7	21	19	27	48	30%	50%

r_1 : If r_1 or fewer responses are observed during Stage 1, the study cohort is stopped early for futility.

n_1 : Number of subjects initially enrolled in the Stage 1.

n_2 : Number of subjects enrolled in the Stage 2.

r : If r or fewer responses are observed by the end of Stage 2, then no further investigation of the drug combination is warranted in the selected tumor type.

n : Total number of subjects.

p_0 : Insufficient response rate.

p_1 : Target response rate.

Table 20: Planned Simon 2-Stage Design with Expansion Stage for PD-1 Refractory SCCHN Cohort in Phase 2

Indication	Combination	r_1	n_1	r_2	n_2	r	n_3	n	p_0	p_1
PD-1 refractory SCCHN	GITR + Nivo	0	12	3	25	6	20	57	5%	20%

Note: The definitions of p_0 , p_1 , r_1 , n , n_1 , and n_2 are the same as those in Table 19.

r_2 : If r_2 or fewer responses are observed by the end of Stage 2, the study cohort is stopped early for futility.

r : If r or fewer responses are observed by the end of expansion stage, then no further investigation of the drug combination is warranted in the study cohort.

n_3 : Number of subjects enrolled in the expansion stage.

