9.3. Level of Significance

For the primary efficacy endpoints, the 1-sided Type I error will be controlled at 0.05 for each individual cohort expansion. Note that this level of significance does not account for the multiple expansion cohorts. For other endpoints, confidence intervals will be reported at a 95% confidence level.

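### The stated Type I error of 0.0231 for the PD-1 refractory SCCHN cohort ignores both futility stops; the three-stage design as written has 0.0172

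*Protocol*

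**What the plan says.** Table 20 in Protocol Section 9.2.2 (Table S6 in the Synopsis) gives the row "PD-1 refractory SCCHN GITR + Nivo 0 12 3 25 6 20 57 5% 20", the last entry being a percentage. The columns are r1, n1, r2, n2, r, n3, n, p0 and p1. The notes to Tables 19 and 20 supply the rules:

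- Stage 1: "If r_1 or fewer responses are observed during Stage 1, the study cohort is stopped early for futility".
- Stage 2: "If r_2 or fewer responses are observed by the end of Stage 2, the study cohort is stopped early for futility".
- End of the expansion stage: "If r or fewer responses are observed by the end of expansion stage, then no further investigation of the drug combination is warranted".

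The text of Section 9.2.2 repeats the Stage 2 rule in firm terms: "the PD-1 refractory SCCHN cohort will be terminated early for futility". Sections 9.4.1.1 and 9.6.1 also word the stops as things that will happen.

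The operating characteristics appear in Section 9.2.2 and again in the Synopsis under Statistical Methods: "With this 3-stage design, the 1-sided Type I error is 0.0231, and the power is approximately 88" per cent. Section 9.3 sets the general limit: "the 1-sided Type I error will be controlled at 0.05 for each individual cohort expansion".

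The SAP does not cover this design. It is based on Protocol Amendment 2 (SAP Section 2.1). The cohort was added in Amendment 4 and is absent from SAP Table 2.

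**The concern.** The sentence attributes both an error rate and a power to one fully specified three-stage design, so both should come out of the same calculation. Only the power does. A mandatory futility stop removes some paths that would otherwise have ended in a positive result, so it lowers the Type I error and the power together. A Type I error computed without the stops cannot sit beside a power computed with them.

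What is at stake is the accuracy of a stated operating characteristic for a test on ORR, the primary Phase 2 endpoint. A reader who compares 0.0231 with the error rates of the Table 19 cohorts would be comparing two conventions without knowing it. Any p-value or confidence interval tied to 0.0231 would be miscalibrated, although neither document plans one.

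**Working it through.** **Inputs** (Protocol Table 20): n1 = 12, n2 = 25, n3 = 20, total 57; r1 = 0, r2 = 3, r = 6; p0 = 0.05, p1 = 0.20. Let X1, X2 and X3 be independent binomial counts on 12, 25 and 20 subjects.

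**Step 1: reproduce the stated error.** With no interim stops, the cohort is declared promising when the total is 7 or more:

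P(X ≥ 7 | n = 57, p = 0.05) = 0.02310.

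This is the stated 0.0231. On the same basis the power is P(X ≥ 7 | n = 57, p = 0.20) = 0.955, which is not the stated 88%.

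**Step 2: Type I error of the design as written.** The quantity needed is P(X1 ≥ 1, X1 + X2 ≥ 4, X1 + X2 + X3 ≥ 7) at p = 0.05.

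- Stop at Stage 1: 0.95^12 = 0.5404.
- Stop at Stage 2 (X1 ≥ 1 but X1 + X2 ≤ 3): 0.3662.
- Enter the expansion stage: 1 − 0.5404 − 0.3662 = 0.0935 (from unrounded values).

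Splitting the 0.0935 by the number of responses among the first 37 subjects:

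| Responses in 37 | Probability | Still needed in 20 | Probability of reaching it | Product |
|---|---|---|---|---|
| 4 | 0.06141 | 3 or more | 0.0755 | 0.00464 |
| 5 | 0.02317 | 2 or more | 0.2642 | 0.00612 |
| 6 | 0.00684 | 1 or more | 0.6415 | 0.00439 |
| 7 or more | 0.00204 | none | 1 | 0.00204 |

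Sum: 0.00464 + 0.00612 + 0.00439 + 0.00204 = **0.01719**. A simulation of 20 million trials gave 0.01725.

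**Step 3: power of the design as written.** The same calculation at p = 0.20 gives Stage 1 stop 0.0687, Stage 2 stop 0.0289, and declared promising **0.8829**. This matches the stated 88%.

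**Step 4: is there a reading that gives both stated figures?**

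| Stops applied | Type I error (p = 0.05) | Power (p = 0.20) |
|---|---|---|
| None | 0.0231 | 0.955 |
| Stage 1 only | 0.0195 | 0.898 |
| Stage 2 only | 0.0196 | 0.932 |
| Both (as written) | 0.0172 | 0.883 |

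No row gives 0.0231 with 88%. Moving r1, r2 or r by one, or reading n2 or n3 as cumulative, does not produce the pair either.

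**Step 5: which convention does the rest of the protocol use?** Table 19 contains five distinct two-stage designs, stated to have a Type I error of 0.05 and a power of 85%.

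| Design (Table 19) | Type I error, stop counted | Type I error, stop ignored |
|---|---|---|
| SCCHN and gastric, doublet | 0.0486 | 0.0745 |
| Cervical, doublet | 0.0487 | 0.0707 |
| Relapsed melanoma | 0.0482 | 0.0579 |
| SCCHN and gastric, triplet | 0.0430 | 0.0551 |
| Cervical, triplet | 0.0471 | 0.0570 |

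Every one meets 0.05 only when its Stage 1 stop is counted. With the stop counted, their power lies between 0.850 and 0.854, as stated.

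**Size of the discrepancy:** 0.0231 − 0.0172 = 0.0059 in absolute terms; 0.02310 / 0.01719 = 1.34, an overstatement of 34%.

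**The case against.** The best defence is that 0.0231 is the Type I error under non-binding futility. Computing the error as if the stops might be overridden is a recognised conservative convention, and it gives a valid upper bound. Some wording, in the Synopsis and Section 4.1.2, speaks of rules that allow for early termination, which could be read as permissive.

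That reading is possible but not documented. Neither document mentions non-binding futility. The operative rules in Sections 9.2.2, 9.4.1.1 and 9.6.1 are worded as mandatory. The Table 19 designs use the opposite convention, and the power in the same sentence holds only if the stops are applied. If the upper bound was intended, it needed a label.

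The objections about consequence do stand. The true error is lower than stated, and both values are below 0.05. The promising or nonpromising decision rests on a count of responses, not on 0.0231. No planned p-value or interval takes 0.0231 as an input: Section 9.3 works with 0.05 per cohort, response rates are reported with 95% intervals, and the two-stage interval method in SAP Section 7.3.2.1 does not depend on it. Amendment 5 records enrollment as complete, so the correction bears on reporting, not on conduct.

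**Conclusion.** The concern holds; the figure is wrong as written. The three-stage design in Table 20 has a one-sided Type I error of 0.0172, not 0.0231, while its stated power of about 88% is right (0.883). The overstatement is conservative and has no effect on the sample size, the stopping boundaries or the conclusion drawn for the cohort.

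This rests on three assumptions: Table 20 gives the intended boundaries, the futility stops are applied as worded, and responses are independent with a common rate. If the stops were meant to be non-binding, 0.0231 would be a correct upper bound, but the power stated beside it would then be on a different basis.

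**What to change.** In Protocol Section 9.2.2 and in the Synopsis, replace 0.0231 with 0.0172 and leave the power as it is. If the sponsor wants to keep the conservative figure, label 0.0231 as ignoring the futility stops and give 0.0172 as the value for the design. Use the same wording in the study report and in any SAP amendment that adds this cohort. The cost is one number in two places, with no change to the design, the data or the analysis.

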9.3. Level of Significance

For the primary efficacy endpoints, the 1-sided Type I error will be controlled at 0.05 for each individual cohort expansion. Note that this level of significance does not account for the multiple expansion cohorts. For other endpoints, confidence intervals will be reported at a 95% confidence level.

9.4. Statistical Analyses

9.4.1. Efficacy Analyses

9.4.1.1. Primary Efficacy Analyses

In Phase 2, the proportion of subjects who meet the objective response criteria (CR + PR) per RECIST v1.1 will be summarized by tumor type.

For the cohorts using a Simon 2-stage design, if there are no responses in each tumor type-specific doublet or triplet treatment group out of the n_1 evaluable subjects specific to that tumor type-specific doublet or triplet treatment group (consistent with a calculated response rate $< p_0$) at Stage 1, then the study will be stopped for futility, and the null hypothesis is not rejected.

Otherwise, in the tumor types in which greater than r_1 responses among the evaluable Stage 1 subjects is observed, where r_1 is also specific to the tumor type and doublet or triplet expansion cohort, an additional n_2 evaluable subjects will be treated in Stage 2. If there are $\leq r$ responders among the evaluable subjects at the end of Stage 2, then the drug will be declared nonpromising for that tumor type within the given doublet or triplet expansion cohort, and the null hypothesis is not rejected. Further investigation of the study drug will be considered interesting (predictive of $\geq p_1$ response rate) if $> r$ responses are observed in the first n evaluable subjects.

For the PD-1 refractory SCCHN cohort using a Simon 2-stage design with an expansion stage, if there is an insufficient number of responses observed at the end of Stage 1 or Stage 2, the cohort will be terminated early for futility. If the number of responders observed is $> r_1$ for Stage 1 and $> r_2$ for Stage 2, an additional number of evaluable subjects needed for the next stage (n_2 and n_3 , respectively) will be enrolled. At the end of the expansion stage, if the number of responders observed is $\leq r$ among the n evaluable subjects, then the drug will be declared nonpromising for the PD-1 refractory SCCHN cohort. If $> r$ responders are observed, the drug will be declared promising for further investigation.

For the hypothesis tests in the Simon 2-stage design and Simon 2-stage design with expansion stage, the null response rate is p_0 and alternative response rate is p_1 , where p_0 and p_1 are specific to the tumor type within a given doublet or triplet expansion cohort and are determined from historical response rates.

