In Phase 2, a Simon 2-stage design will be run for the cervical cancer, gastric cancer, SCCHN and PD-1/PD-L1 relapsed melanoma cohorts within a given doublet or triplet treatment group. The planned Simon 2-stage designs are summarized in [Table S5](#), assuming a 1-sided Type I error of 0.05 and power of 85%. Each Simon 2-stage design will have a stopping rule to allow early termination of a particular tumor type within the given drug combination at the end of Stage 1 if there is insufficient response observed (calculated response rate $< p_0$), while enrolling enough subjects to predict possible target responses ($\geq p_1$) worthy of cohort expansion and potentially further evaluation in future studies.

Table S5: Planned Simon 2-Stage Designs for Phase 2

Indication	Combination	r_1	n_1	r	n_2	n	p_0	p_1
SCCHN	GITR + Nivo	3	16	10	30	46	15%	35%
Gastric	GITR + Nivo	3	16	10	30	46	15%	35%
Cervical	GITR + Nivo	4	17	14	34	51	20%	40%
Relapsed melanoma	GITR + Nivo	2	20	8	30	50	10%	25%
Relapsed melanoma	GITR + Ipi	2	20	8	30	50	10%	25%
SCCHN	GITR + Nivo + Ipi	5	18	17	32	50	25%	45%
Gastric	GITR + Nivo + Ipi	5	18	17	32	50	25%	45%
Cervical	GITR + Nivo + Ipi	7	21	19	27	48	30%	50%

r_1 : If r_1 or fewer responses are observed during Stage 1, the study cohort is stopped early for futility.

n_1 : Number of subjects initially enrolled in the Stage 1.

n_2 : Number of subjects enrolled in the Stage 2.

r : If r or fewer responses are observed by the end of Stage 2, then no further investigation of the drug combination is warranted in the selected tumor type.

n : Total number of subjects.

p_0 : Insufficient response rate.

p_1 : Target response rate.

For the PD-1 refractory SCCHN cohort in doublet Treatment Group F, a Simon 2-stage design with an expansion stage, summarized in [Table S6](#), will be used. With this 3-stage design, the 1-sided Type I error is 0.0231, and the power is approximately 88%. The PD-1 refractory SCCHN cohort will be terminated early for futility at the end of Stage 1 or Stage 2 if there is insufficient response observed. At the end of the expansion stage, if there is sufficient response observed, the doublet schedule for the PD-1 refractory SCCHN cohort will be declared promising for further investigation; otherwise it is considered nonpromising.

Table S6: Planned Simon 2-Stage Design With Expansion Stage for PD-1 refractory SCCHN Cohort in Phase 2

Indication	Combination	r_1	n_1	r_2	n_2	r	n_3	n	p_0	p_1

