9.6. Interim Analysis

9.6.1. Simon 2-Stage Design and Simon 2-Stage Design With an Expansion Stage

In Phase 2, the Simon 2-stage design will be applied for the cervical cancer, gastric cancer, SCCHN, and PD-1/L-1 relapsed melanoma cohorts within a given doublet or triplet treatment group, and the Simon 2-stage design with an expansion stage will be used for the PD-1 refractory SCCHN cohort in the doublet combination of INCAGN01876 and nivolumab (Treatment Group F). If insufficient responses are observed in any stage, then the cohort will be discontinued. As discussed in Section 9.2.2, the Simon 2-stage designs and the Simon 2-stage design with an expansion stage have design parameters that are determined by historical response rates and will have different sample sizes and different futility rules, depending on the historical response rate determined by different tumor types and different drug combinations.

As an example, the probability of early termination for Stage 1 in the head and neck tumor cohort for the doublet combination of INCAGN01876 and nivolumab is summarized in Table 23. If at least 4 responses are observed in the first evaluable 16 subjects, then 30 additional evaluable subjects will be enrolled in this cohort (Stage 2).

Table 23: Probability of Early Termination of Stage 1 for Simon 2-Stage Design

True Response Rate	Probability of Early Termination at Stage 1
15%	79.0%
20%	59.8%
25%	40.5%
30%	24.6%
35%	13.4%

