#### **9.1.2. Interim Analyses for Futility**

##### **9.1.2.1. Simon 2-Stage Futility Rules**

An interim analysis of efficacy will be conducted in Phase 2 by applying the Simon 2-stage design for each tumor within a given treatment group. During Stage 1,  $n_1$  evaluable subjects treated at the recommended dose and schedule will be enrolled, and if  $r_1$  or fewer responses (Table 2) are observed by the Week 16 assessment, then the cohort will be discontinued. To be counted as evaluable for the calculation in Stage 1, subjects must have discontinued from the study, reached the Week 16 assessment, or had at least 2 scans. As discussed in Section 3.2, the Simon 2-stage designs conducted for each tumor type within each treatment group have design parameters that are determined by historical response rates and will have different sample sizes and futility results depending on the historical response rate.

As an example, the probability of early termination for Stage 1 in the SCCHN tumor cohort for the doublet combination of INCAGN01876 and nivolumab in Treatment Groups F, G, and H is

summarized in [Table 11](#). If at least 4 responses (CR or PR) are observed in the first evaluable 16 subjects, then 30 additional evaluable subjects will be enrolled in this cohort for Stage 2.

[figure not shown]
Per mRECIST v1.1, the tumor response should be confirmed by a repeat radiographic assessment not less than 4 weeks from the date that the first response was documented. Disease progression will be confirmed by a second tumor assessment in at least 4 weeks and no later than 6 weeks after the first scan indicating PD in clinically stable subjects. The first tumor assessment is conducted in the eighth week. If a CR or PR occurs after an unconfirmed PD in at least 4 weeks but no more than 6 weeks, then the tumor assessment will be counted as a corresponding CR or PR (Section [7.3.2.3](#)).

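### Protocol 9.4.1.1 sets the Stage 1 futility stop for the Table 19 cohorts at zero responses, not r1 or fewer, so 1 to r1 responses have no stated outcome there

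*Protocol*

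**What the plan says.** Protocol 9.4.1.1 (Primary Efficacy Analyses) covers the cohorts that use a Simon 2-stage design. The Stage 1 stop, and the statement that the null hypothesis is not rejected, apply "if there are no responses in each tumor type-specific doublet or triplet treatment group out of the" n1 evaluable subjects. A parenthesis describes this as consistent with a calculated response rate below p0, and the text says that the study is stopped. The next paragraph gives the condition for Stage 2, which is more than r1 "responses among the evaluable Stage 1 subjects is observed, where" r1 is specific to the tumor type and combination.

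The rule is stated differently elsewhere:

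- Protocol Table 19 legend: if r1 "or fewer responses are observed during Stage 1, the study cohort is stopped early for futility".
- Protocol 9.2.2, which sets the cut at r1 and then closes enrolment: "or fewer responses in the cohort, it will be concluded that the true response rate is unlikely to be greater than or equal".
- Protocol 9.6.1, SCCHN doublet example (r1 = 3): "If at least 4 responses are observed in the first evaluable 16 subjects, then 30 additional evaluable subjects will be enrolled in this cohort".
- SAP 9.1.2.1: if r1 "or fewer responses (Table 2) are observed by the Week 16 assessment, then the cohort will be discontinued".

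The Synopsis and 9.2.2 also describe the stop in terms of the observed rate. The Synopsis refers to termination within "the given drug combination at the end of Stage 1 if there is insufficient response observed (calculated response rate" below p0), and 9.2.2 uses nearly the same words.

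**The concern.** In Table 19, r1 is 2, 3, 4, 5 or 7, so zero responses and r1 or fewer coincide in no row. The only design with r1 = 0 is the PD-1 refractory SCCHN cohort (Table 20), which has its own paragraph in 9.4.1.1 and is not affected.

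Read on its own, 9.4.1.1 leaves a hole. With 1 to r1 responses, the stop condition is not met, the Stage 2 condition is not met, and nothing is said about the null hypothesis. The gloss about a rate below p0 does not fill the hole, because it sets a different cut again.

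This section governs the primary efficacy analysis. The Amendment 5 rationale in Appendix C says that enrolment is complete, so what remains at stake is which rule is applied and reported for a cohort that ended Stage 1 with 1 to r1 responses. The SAP is only a partial backstop. It is based on Amendment 2, and its Table 2 has endometrial, gastric and SCCHN rows but none for cervical cancer or relapsed melanoma. For those two indications r1 comes from the Protocol alone.

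**Working it through.** **Inputs.** r1, n1, r, n2, p0 and p1 are from Protocol Table 19. The design targets, from 9.2.2, are a 1-sided Type I error of 0.05 and power of 85%. X is the Stage 1 response count, Binomial(n1, p).

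**Formulas.**

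- Early termination with cut c: P(X ≤ c).
- Omitted outcome: P(1 ≤ X ≤ r1) = P(X ≤ r1) − P(X = 0).
- Rejection of the null with cut c: the sum over x > c of P(X = x) × P(Y ≥ r + 1 − x), where Y is Binomial(n2, p). This is Type I error at p0 and power at p1.

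**The plan's own figure.** Protocol Table 23 gives early termination for the SCCHN doublet at true rates of 15, 20, 25, 30 and 35% as 79.0, 59.8, 40.5, 24.6 and 13.4%. P(X ≤ 3) with n1 = 16 gives 0.7899, 0.5981, 0.4050, 0.2459 and 0.1339, which agrees throughout. A zero-response stop at 15% would give 0.85^16 = 0.074, so Table 23 was built on r1 = 3.

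**Size of the omitted outcome.**

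| Design | r1/n1 | P(X ≤ r1) at p0 | P(X = 0) at p0 | P(1 to r1) at p0 | P(1 to r1) at p1 |
|---|---|---|---|---|---|
| Doublet SCCHN, gastric | 3/16 | 0.790 | 0.0743 | 71.6% | 13.3% |
| Doublet cervical | 4/17 | 0.758 | 0.0225 | 73.6% | 12.6% |
| Relapsed melanoma | 2/20 | 0.677 | 0.1216 | 55.5% | 8.8% |
| Triplet SCCHN, gastric | 5/18 | 0.717 | 0.0056 | 71.2% | 10.8% |
| Triplet cervical | 7/21 | 0.723 | 0.0006 | 72.2% | 9.5% |

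**The rate-below-p0 wording.** The largest counts with an observed rate below p0 are 2/16, 3/17, 1/20, 4/18 and 6/21, in the same order. Each is r1 − 1. For melanoma, 2/20 equals p0 = 10% exactly, so r1 responses do not satisfy the gloss.

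**Type I error under each wording.** Here r is unchanged, cohorts above the cut are assumed to continue, and the separate Bayesian rule is set aside.

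| Design | Stop at ≤ r1 | Stop at rate < p0 | Stop at 0 |
|---|---|---|---|
| Doublet SCCHN, gastric | 0.0486 | 0.0645 | 0.0743 |
| Doublet cervical | 0.0487 | 0.0617 | 0.0707 |
| Relapsed melanoma | 0.0482 | 0.0555 | 0.0576 |
| Triplet SCCHN, gastric | 0.0430 | 0.0505 | 0.0551 |
| Triplet cervical | 0.0471 | 0.0533 | 0.0570 |

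Power is 0.850 to 0.854 with the r1 rule and 0.903 to 0.961 with a zero-response stop. Under p0, expected enrolment per cohort rises from 22.3–29.7 with the r1 rule to 43.8–50.2 with a zero-response stop.

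**Does the Bayesian futility rule close the gap?** Protocol 9.6.2 applies it to cervical, gastric and SCCHN, which is 12 of the 14 Table 19 cohorts (three tumor types in each of Groups F, H, J and L). As a rough check I assumed one look at n1, prior probability of activity 0.4 (the SAP value) and no borrowing. The probability of success is then below 20% at up to 2/16, 3/17, 5/18 and 7/21. That returns the triplets to 0.043 and 0.047 but leaves the doublets at 0.062 to 0.065. The real rule borrows across cohorts and is repeated at each enrolment, so these figures are only indicative. The two melanoma cohorts have no such rule. For them the comparison is 0.058 against 0.048, with early stopping of 12.2% against 67.7%.

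**The case against.** The strongest reply is that the rule is not in doubt. The Synopsis table legend, 9.2.2, the Table 19 legend, 9.6.1 with Table 23, and the SAP text and simulations all use r1, and one phrase is out of line. That stands: the Protocol as a whole does supply a stop for 1 to r1 responses, and Table 19 is correct.

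Second, 9.4.1.1 itself bars the harmful reading, because Stage 2 opens only above r1. That also stands. The higher Type I errors describe a procedure that no section permits, and they are conditional figures only.

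Third, r1 is smaller than r in every row, so a cohort that stopped with 1 to r1 responses cannot exceed r and cannot reject the null. This is right, and it limits the consequence for cohorts that did stop. It does not supply the missing statement.

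Fourth, the p0 parenthesis may be explanation rather than a cut-off. Even so, it is wrong as an explanation, because r1/n1 is at or above p0 in every row. Power is not at risk under either alternative wording; Type I error is.

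**Conclusion.** The concern holds. Protocol 9.4.1.1 misstates the Stage 1 threshold for every Table 19 cohort and gives no disposition for an outcome that is more likely than not under p0 (55.5% to 73.6%). These probabilities are exact binomial and rest only on the Table 19 parameters.

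The intended rule can be recovered from the rest of the Protocol, and it is the only one of the three wordings that keeps Type I error at or below 0.05. The excess under the others (0.0505 to 0.0645 for the p0 wording, 0.055 to 0.074 for zero responses) would arise only if cohorts were continued against the section's own Stage 2 condition and with the Bayesian rule set aside. Nothing in the documents shows that this happened. It should be corrected because it sits in the primary-analysis section, but it does not undermine the design.

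**What to change.** - **Protocol 9.4.1.1:** replace the zero-response condition and its p0 parenthesis with *r1 or fewer responses among the n1 evaluable subjects*. Keep the conclusion that the null hypothesis is not rejected. Say that the cohort, not the study, is stopped, since a single-cohort rule should not read as a study-wide one.
- **Synopsis (Statistical Methods) and Protocol 9.2.2:** replace the parenthesis about a response rate below p0 with *r1 or fewer responses*.

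The cost is three sentences. No patients, data or analyses are added, and the Protocol then agrees with its own Table 19 and with the rule in SAP 9.1.2.1. SAP Table 2 would still lack cervical and melanoma rows. For any cohort that closed after Stage 1, the report should give the response count alongside r1 and state that the null hypothesis was not rejected.
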